- When possible, a small quantity of maternal and newborn hair will be removed from the scalp as close to delivery as possible for determination of buprenorphine and metabolites.
- In the nursery, the infant will undergo standard newborn testing for signs of neonatal withdrawal (Neonatal Abstinence Syndrome, NAS). The duration and intensity of treatment will be recorded.

Maternal and umbilical cord blood and maternal and infant hair concentrations of BUP and its major metabolites will be determined by mass spectrometry. We will determine maternal cord blood concentration ratios and hair concentrations of buprenorphine and related concentrations to the severity of neonatal withdrawal symptoms.

For Specific Aim 6: Subjects who are breastfeeding and undergoing the postpartum pharmacokinetic study will also be asked to provide breast milk samples for estimation of total amount of BUP and its metabolites secreted. On this PK study day, subjects will be asked to pump the breast just prior to taking the study dose of BUP. Subjects will then take the BUP dose. Approximately every 2-4 hrs. after BUP administration, breast milk will be pumped using a breast pump and total volume measured. An aliquot of at least 1 ml but no more than 5 ml will be saved for analysis of BUP and its metabolites, and the rest of the milk will be returned to the mother for feeding the baby. In those women consenting, we will also obtain one heel stick blood sample prior to a feeding and another sample 1 hour after the feeding. Optimally, this will be done during the feeding that is as close as possible to the mother's BUP dose.

We will also perform another elective ancillary study while the baby is hospitalized or during routine postpartum PRC appointments to evaluate the time of appearance of BUP in breast milk and to assess how much drug gets into the baby's blood. We will study postpartum women who are

breast feeding and will request 1-3 samples (at least 1 ml but no more than 5 ml each) of the mother's milk for analysis of BUP. We will request 2 infant heel stick samples with each breast milk collection. One heel stick sample will be collected prior to a breast feeding (trough level) and another one 1 hour after the feeding (peak level).

D.2. Primary Research Question

The primary research questions are whether BUP and metabolite exposure (reflected as the dose-adjusted AUC) differs during pregnancy and between pregnancy and the postpartum state.

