No attempt will be made to mandate clinical management of the subjects. If complications arise, the patient will still be eligible for additional PK studies unless the complication affects the pharmacology of BUP i.e. significant liver or renal disease.

If a patient who consented to any part of this study (Parts A-E) is dismissed from her Medication Assisted Treatment (MAT) clinic due to non-compliance, she will be dismissed from the study and another subject will be recruited to replace her.

If non-prescribed opiates/opioids are detected during any PK screening visits, the subject will be ineligible to complete the pending PK visit. Subjects may be re-screened at a later date as long as they are within the gestational window for the PK visit. If a subject in the PK study has two positive drug screens for non-prescribed opiates/opioids during any screening visits, she will be dismissed from the study and replaced with another study subject.

At the time of enrollment, patients will consent to those components of the study that they wish to participate in. Subjects are required to complete at least one PK study in order to participate in this portion of the study. If a subject consents to portion of the study and they are unable to complete it within the acceptable timeline, they will still be eligible to participate in the remaining

parts of the study they consented to.

D.5.iv. Study PK Visits:

Once the subject has signed the consent form, completed the Screening Visit, and is deemed eligible for the study, the research staff will establish a schedule for the subject to undergo their first PK study. Subjects participating in the PK study must complete at least one PK study.

Screening Visits will be conducted within 1-2 weeks prior to each PK study and subjects must continue to meet the criteria listed in section D.4, with the exception of exclusion criteria items 6 and 7. A urine drug screen (Immunoassay) will be performed on the day of the PK study.

Each PK study, both during and after pregnancy, will be performed after the subject has been on a consistent two, three, four, or five time daily dose of BUP for a minimum of 7 days.

D.5.v. BUP Administration During PK Visit:

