The following collection and processing instructions apply to all blood and saliva samples collected during this study. The samples collected will be dependent on which parts of the study the subject participates in.

Blood samples will be collected as follows:

- Maternal and Cord Blood Samples for BUP Analysis: One 10 mL heparinized vacutainer tube will be drawn at the time points described in sections D.5.vi and D.5.ix. The tube should be centrifuged at 1500 g at 4°C for 15 minutes. Plasma samples will then be transferred into polypropylene tubes and frozen at -80 degrees centigrade until analysis.
- PBMC analysis: One 5 mL EDTA vacutainer tube will be drawn with the first sample (pre-dose) at each PK study visit and at delivery (applicable to all subjects), when possible. The sample should be stored at room temperature. Notify [name] lab in advance at [contact] / [contact] or via email ([contact]) to allow for pick up and processing within 4 hours of collection.
- DNA Analysis: One 10 mL EDTA vacutainer tube will be drawn at the Baseline Screening Visit. If the DNA sample is unable to be obtained at the screening visit, it may be collected anytime during the study when blood is being drawn. The sample should be frozen at -80 degrees centigrade until analysis.

Saliva samples will be collected using a Sarstedt Salivette collection device. The salivary collection sponge can be centrifuged later in the day. Salivary pH will be determined. Oral fluid samples will then be transferred into polypropylene tubes and frozen at -80 degrees centigrade until analysis.

D.5.xii. Study Outcome Measures and Ascertainment (Applicable to all Subjects):

Mothers and infants will be followed until they are discharged from the hospital, at which time relevant data from the labor, delivery and nursery records will be recorded.

a. Primary Outcome:

The primary outcome is the exposure to BUP (AUC) during pregnancy and the post-partum state.

b. Secondary Outcomes Maternal:

Other maternal outcomes to be measured are:

1. The relationship between COW and Craving scores, pupillometry, heart rate, blood pressure

and GSR scores to the maternal plasma concentration of BUP and its major metabolites

2. The impact of polymorphisms of CYP 450 and conjugating enzymes of buprenorphine on plasma concentration of BUP and its major metabolites
3. The relationship between the umbilical cord and maternal concentration of BUP and its major metabolites

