4. The relationship between maternal dose and concentration of buprenorphine and metabolites in umbilical cord, maternal and infant hair
5. The relationship between maternal plasma and breast milk concentrations of BUP and major metabolites
6. Cumulative amount of BUP and its metabolites excreted in breast milk.

c. Secondary Outcomes Neonatal:

Neonatal outcomes to be measured include the following:

1. Relationship between concentrations of BUP and its metabolites in maternal and umbilical cord plasma and maternal and newborn hair and maternal dose and parameters of neonatal withdrawal
2. Infant hospital days
3. Birthweight
4. Gestational age
5. Neonatal Complications including: Respiratory distress syndrome (RDS), stillbirth, neonatal death, intraventricular hemorrhage as determined by cranial ultrasound, bronchopulmonary dysplasia, necrotizing enterocolitis, early onset of neonatal sepsis, seizures, retinopathy of prematurity (ROP), and hyperbilirubinemia.

D.5.xiii. Statistical Considerations

Data Analysis Plan:

The primary outcomes will be the area under the plasma concentration x time curve (AUC) of BUP during early pregnancy compared to the AUC in late pregnancy. We will also compare the AUC of BUP and metabolites during early and late pregnancy and the post-partum period. Mixed-effect models, repeated measures ANOVA or paired t-testing, will be used to compare early to late-pregnancy and overall pregnancy values to the postpartum values. Secondary outcomes such as metabolite concentrations will be analyzed in the same fashion. Additional analysis will also include multiple regressions to evaluate the relationships between maternal and fetal plasma concentrations of BUP and its metabolites, placental p-glycoprotein, physiologic parameters and CYP3A4/5 expression. We will also use population pharmacokinetic analysis to evaluate the contribution of various covariates (i.e. maternal genotype, BMI, etc.) to the observed variability in the trough plasma concentrations of BUP.

Primary Hypothesis

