Based on data from our recently completed study, the dose-adjusted AUC was 2.34 ± 1.82 (ng/ml).hr in pregnant women at a mean gestational age of 34 weeks. In postpartum women, the dose adjusted AUC was nearly 100% higher at 4.0 ± 2.8 (ng/ml).hr. We anticipate that the AUC in the first half of pregnancy will be somewhere between values of non-pregnant women and those of pregnant women in the latter part of pregnancy. The sample size required to demonstrate a 50% difference between the dose adjusted AUC in the first half of pregnancy and the second half of pregnancy as well as a 50% difference between the dose adjusted AUC in the first half of pregnancy and the postpartum state is 37 ($\alpha = 0.05$, $\beta = 0.80$). We will recruit an additional 3 subjects to

account for dropouts or noncompliance. The secondary physiological outcomes will also be addressable with this sample size as the variance in pupil measurements is small (4.65 ± 0.4 mm at baseline and 2.64 ± 0.08 mm at 2 hours in the paper of Middleton et al¹³) and each patient will provide data from 2-3 PK studies. Thus there will be 120 studies that relate a physiologic variable to plasma buprenorphine. Specific Aim 5 which relates NAS to various parameters (maternal dose, maternal and cord plasma buprenorphine /metabolite concentrations etc.) can be addressed with the projected sample size as correlations between the dependent variable NAS and the numerous independent variables i.e. maternal dose, maternal concentration at delivery, maternal hair concentration, cord blood concentration, newborn hair concentration etc. can be performed with samples size of 15. We assume that 50 % of these infants will have some degree of NAS so the sample size of 40 should be sufficient. If the prevalence of NAS is lower, we can recruit additional subjects. Since the extensive PK studies will not be required to test this hypothesis, recruitment should be easier and can be done at secondary sites if needed.

Secondary Hypotheses

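### The primary question and sample size use dose-adjusted AUC, but the Primary Outcome and Data Analysis Plan name plain AUC, although a woman's dose and dosing frequency may change between visits

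*Combined protocol and SAP*

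**What the plan says.** The protocol describes its primary variable in five places.

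- **D.2, Primary Research Question:** whether "BUP and metabolite exposure (reflected as the dose-adjusted AUC) differs during pregnancy and between pregnancy and the postpartum state".
- **D.5.xii.a, Primary Outcome:** "The primary outcome is the exposure to BUP (AUC) during pregnancy and the post-partum state".
- **D.5.xiii, Data Analysis Plan:** the primary outcomes are the "area under the plasma concentration x time curve (AUC) of BUP during early pregnancy compared to the AUC in late pregnancy". The methods follow: "Mixed-effect models, repeated measures ANOVA or paired t-testing, will be used to compare early to late-pregnancy", and overall pregnancy with postpartum. No dose term is named. On metabolites it adds: "Secondary outcomes such as metabolite concentrations will be analyzed in the same fashion".
- **D.5.xiii, Primary Hypothesis:** the study is sized on a "50% difference between the dose adjusted AUC in the first half of pregnancy and the second half of pregnancy", and on the same difference between early pregnancy and postpartum. The pilot means quoted there are dose-adjusted.
- **D.6, Preliminary Data:** under a heading that ties it to the primary outcome, it reports dose-adjusted AUC in the third trimester and postpartum.

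On dosing, D.5.iii says: "No attempt will be made to mandate clinical management of the subjects". D.5.iv requires a consistent regimen of two to five doses a day for at least 7 days before each PK study. D.5.v has each woman take her own prescribed drug. Section A foresees that a lower dose may be needed postpartum. D.5.vi ends sampling at 12, 8, 6 or 5 hours for two, three, four or five doses a day.

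**The concern.** The two sections that define and analyse the endpoint omit the dose adjustment that the question and the sample size rely on. This would matter little if each woman kept one regimen throughout, but no passage requires that.

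The study asks whether the body handles the drug differently as pregnancy advances and after delivery. Prescribed dose may move over the same period, possibly in response to the same physiology. If the dose is higher at the visit where exposure per mg is lower, a comparison of plain AUC understates the pregnancy effect; if it is lower there, the comparison exaggerates it. A change in frequency also changes the length of the sampled interval. Clearance (CL/F) and the population model do account for dose, but D.5.xiii places both under Secondary Hypotheses.

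**Working it through.** **1. The passages side by side**

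| Place | Variable | Dose-adjusted? |
|---|---|---|
| D.2 | BUP and metabolite exposure | Yes |
| D.5.xii.a | BUP AUC | Not stated |
| D.5.xiii, Data Analysis Plan | BUP AUC | Not stated |
| D.5.xiii, Primary Hypothesis | AUC | Yes, for the sized differences and pilot values |
| D.6 | AUC | Yes |

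**2. The plan's own figure.** Inputs from the Primary Hypothesis: late-pregnancy mean 2.34 and SD 1.82, both dose-adjusted; a 50% difference, so 0.5 × 2.34 = 1.17; alpha 0.05, taken as two-sided; and the stated 0.80 read as power. The two-sample formula gives

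n = 2 × (1.960 + 0.842)² × 1.82² / 1.17² = 37.98, or 38 per group,

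against the stated 37. The plan's comparison is within women and it gives no within-woman SD or correlation, so the exact route to 37 cannot be identified. The result is enough to show that dose-adjusted inputs lead to about the stated number.

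**3. Effect of a dose change.** Assume steady state and dose-proportional kinetics. Dosing-interval AUC is then dose ÷ (CL/F), so

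plain-AUC ratio = dose-adjusted ratio × dose ratio.

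The dose ratios below are assumed and common to all women; the documents give none.

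*Early/late, true dose-adjusted ratio 1.5 (the sized 50% read as a ratio):*

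- late dose 1.1 times early: 1.5 / 1.1 = 1.36
- late dose 1.25 times early: 1.5 / 1.25 = 1.20
- late dose 1.5 times early: 1.5 / 1.5 = 1.00
- late dose 0.8 times early: 1.5 / 0.8 = 1.88

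*Late pregnancy/postpartum, pilot ratio 2.34 / 4.0 = 0.585 (not one of the contrasts that was sized):*

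- pregnancy dose 1.25 times postpartum: 0.585 × 1.25 = 0.73
- pregnancy dose 1.5 times postpartum: 0.585 × 1.5 = 0.88
- pregnancy dose 1.71 times postpartum: 0.585 × 1.71 = 1.00

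**4. Effect of a frequency change.** Suppose the daily dose and clearance stay the same, doses are equal and evenly spaced, and a woman moves from two to four doses a day. Each dose halves and the window falls from 12 to 6 hours, so plain interval AUC halves (ratio 0.5) with no change in the pharmacology. Dividing by the single dose removes this. So does scaling AUC to 24 hours and dividing by the daily dose. Dividing a single-interval AUC by the daily dose does not: the ratio stays at 0.5. The interval and the divisor must therefore be defined together.

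**5. Whether one matched definition is clearly better.** Inputs: a one-compartment model at steady state with bolus input, k = ln 2 / half-life, and first interval τ. Let a_i be the hours since dose D_i at the time of the morning dose D₁. Then

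AUC × CL = Σ D_i e^(−k·a_i) × (1 − e^(−kτ)) / (1 − e^(−24k)).

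Version S divides this by D₁. Version T multiplies it by 24/τ and divides by the daily dose. The ideal value of each is 1.

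- Section A's 22 h half-life, equal doses, assumed waking-hour schedules (0/10; 0/6/12; 0/5/10/15; 0/4/8/12/16 h): S = 0.84, 0.73, 0.81, 0.80; T = 1.00, 0.97, 0.97, 0.96.
- 22 h, two doses 12 h apart in ratio 2:1, larger or smaller first: S = 0.80 or 1.41; T = 1.06 or 0.94.
- Assumed 3 h half-life, same 2:1 doses: S = 0.97 or 1.06; T = 1.29 or 0.71.

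Version T is closer to 1 in every case at 22 h. Version S is closer with a short half-life and unequal doses.

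**The case against.** The case for reading plain AUC as shorthand is strong. D.2 defines exposure through dose-adjusted AUC, and the Primary Outcome reuses the word exposure. The Primary Hypothesis sits in the same section as the Data Analysis Plan. D.6 presents dose-adjusted values as the data relevant to the primary outcome. The shorthand also recurs: among dose-adjusted figures the Primary Hypothesis writes "We anticipate that the AUC in the first half of pregnancy will be somewhere between values of non-pregnant women", and D.6 gives a CV for plain AUC directly after dose-adjusted means. All of this stands, and dose-adjusted AUC is the likely intent. It does not remove the problem, because neither operative passage refers back to D.2 and no passage gives the divisor or ties it to an interval. The sampling schedule only suggests the interval, and D.5.xiii lists AUC(0-t) and AUC(0-∞) without choosing between them.

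A reader might infer more than the documents support:

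- **That the sample size is wrong.** It already rests on dose-adjusted AUC.
- **That a stated amount of power is lost.** The documents give no SD for plain AUC and no distribution of dose changes. A power figure would have to borrow the dose-adjusted CV and assume one dose factor for all women.
- **That a primary contrast is missing.** D.2, the Data Analysis Plan and the Primary Hypothesis each cover both change within pregnancy and the comparison with postpartum.
- **That dose goes unrecorded after the first visit.** D.5.ii marks only the screening blood sample, with its dosing history, as first PK study only. CL/F and the dose covariate in D.5.xiii imply that dose is known at each visit. The plan does not say so explicitly.
- **That the analysis must be on the log scale.** A raw paired t-test is valid here. The log scale is a preference.

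**Conclusion.** The inconsistency is real and concerns the primary endpoint. It should be fixed, although the remedy is small. Taken as written, D.5.xii.a and the Data Analysis Plan would confound the pregnancy effect with changes in dose and dosing interval. The likely intent is the dose-adjusted measure, so this is a defect in the operative definition and not evidence that the sponsor means to compare plain AUC.

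The size of any bias cannot be estimated from the documents. Under the assumptions in step 3 of the working, a late dose 1.5 times the early dose would hide the whole sized difference, and a pregnancy dose 1.71 times the postpartum dose would hide the whole pilot difference. These are illustrations, not forecasts. The inconsistency itself depends on none of these assumptions.

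**What to change.** 1. In D.5.xii.a and the Data Analysis Plan of D.5.xiii, replace AUC with dose-adjusted AUC of BUP as the primary variable. Keep metabolites secondary, as the Data Analysis Plan has them, and align D.2 on that point.
2. Define the variable in one sentence so that it is comparable across dosing frequencies. Use either dosing-interval AUC divided by the dose taken, or AUC scaled to 24 hours divided by total daily dose. Name one as primary and the other as a sensitivity analysis. The calculation in step 5 can inform the choice but does not settle it.
3. Report plain AUC descriptively.
4. State that dose and dose times are recorded at every PK visit.

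The cost is slightly more data recording and one extra sensitivity analysis. No extra samples are needed, and 37 (+3 = 40) stands. A log-scale model, a ranking of the contrasts and a particular divisor are optional improvements, not corrections of an error.

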We will enroll eligible, consenting pregnant women who are receiving sublingual BUP (subutex) in a supervised hospital or outpatient clinical setting because of their opiate addiction. Due to the possibility of limited subject availability at individual centers, recruitment can target subjects receiving pregnancy care at other institutions. Likewise, since buprenorphine is commonly not dispensed in a hospital setting, subjects may need to be recruited from clinics where buprenorphine is provided to pregnant women as part of a structured maintenance program. To facilitate enrollment, recruitment can target one or more specific aims as summarized below.

For Specific Aims 1 and 3:

We will recruit 40 eligible, consenting pregnant women to an 'extensive sampling' pharmacokinetic (PK) study in which they will be studied three times: once between 8 0/7-20 6/7, once between 21 0/7-35 6/7 and once at 4-6 weeks post-delivery. Studies done during pregnancy should be at least 12 weeks apart. We will also obtain patient demographics and medical history.

We will encourage subjects to complete as many PK studies as possible; however, subjects are only required to complete one PK study in order to participate in this portion of the study. Each study is 13 hours in length for BID dosing, 9 hours for TID dosing, 7 hours for QID dosing, and 6 hours for five times daily dosing.

Each PK study will be performed after the subject has been on a stable dose of BUP for a minimum of 7 days. Physiologic testing (pupillometry, galvanic skin response, and heart rate), COW and craving scores will be performed before the daily dose of BUP is taken.

Measurement Type	Dosing	Length of Study	No. of Measurements
Blood (BUP/metabolite)	BID	13 hrs	Baseline + 12 additional
Physiologic			Baseline + 9 additional
Blood (BUP/metabolite)	TID	9 hrs	Baseline + 12 additional
Physiologic			Baseline + 9 additional
Blood (BUP/metabolite)	QID	7 hrs	Baseline + 10 additional
Physiologic			Baseline + 7 additional
Blood (BUP/metabolite)	5 times/daily	6 hrs	Baseline + 10 additional
Physiologic			Baseline + 7 additional

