D.3. Secondary Research Questions

This study will also attempt to address the following questions recognizing that an inadequate sample size may be available for some of these outcomes:

1. How quickly do buprenorphine trough concentrations decrease after delivery?
2. What maternal covariates impact the plasma concentration of BUP and its metabolites?
3. Is there a pharmacodynamic parameter that reflects maternal satiety and withdrawal?
4. What is the relationship between maternal BUP and metabolite concentrations and cord blood concentrations and NAS risk?
5. What is the infant's exposure to BUP through breast milk?
6. How quickly in the postpartum period does BUP appear in breast milk?
7. How well does cotinine concentration relate to smoking reported by the subject on the smoking questionnaire?
8. Does smoking modify the relationship between physiologic measures and plasma buprenorphine concentrations?
9. Does smoking impact the risk of NAS?
10. How well do catecholamine concentrations reflect physiologic parameters and satiety?

D.4. Study Design

This will be a multicenter pharmacokinetic (PK) and pharmacodynamic (PD) study of sublingual BUP in pregnant women on the medication for their drug addiction. There are several parts to this study and subjects may participate in one or more parts, as described below.

For subjects that choose to participate in procedures other than the PK studies (Parts B-E), only minimal testing is required prior to coming to the hospital for delivery. Blood samples for BUP determination and DNA (deoxyribonucleic acid) analysis will be obtained at the time of consent.

Part A: Subjects will participate in PK studies that will occur at 2-3 different times during the study: 1) between 8 and 20 weeks of pregnancy; 2) between 21 and 35 weeks of pregnancy; and 3) between 4 to 6 weeks postpartum. There will be a minimum of 12 weeks between PK visits during pregnancy. Subjects must complete at least one PK visit in order to participate in this portion of the study.

Part B: Prior to delivery, we will collect maternal blood samples. At the time of delivery, we will collect a cord blood sample, a 3 x 3 cm placental sample, and a 3 inch umbilical cord sample.

Part C: Hair samples from the mother and baby collected within 3 days after delivery

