Part D: While the baby is hospitalized, we will request 1-3 samples (at least 1 ml but no more than 5 ml each) of the mother's breast milk for analysis of BUP. We will collect 2 infant heel stick samples with each breast milk collection. One heel stick sample will be collected prior to a breast feeding (trough level) and another one 1 hour after the feeding (peak level).

Alternatively, subjects may also elect to participate in Part D during 1-3 routine postpartum PRC appointments, as long as they are still taking Buprenorphine (Subutex or Suboxone). The research staff will work with the patient to coordinate the sample collection with the timing of the patient's last BUP dose.

During each visit, we will request an infant heel stick sample prior to a breast feeding (trough level). The subject will then collect a breast milk sample. We will reserve a sample of at least 1 ml but not more than 5 ml for analysis of BUP and return the remainder to the mother for her infant. We will then collect a second infant heel stick sample 1 hour after the feeding (peak level). Ideally, we will collect both breast milk and heel stick samples during each collection; however, it is acceptable to collect only breast milk samples if the mother does not consent to the collection of heel stick samples.

Part E: We will collect 1-2 maternal blood samples while the patient is in the hospital, at least 2 days apart. We will continue to collect maternal blood samples during the subject's routine visits to the MWH BUP clinic weekly for the next 4 weeks. The time of the blood draw, the time of the last dose administration, and the dosing history will also be recorded.

D.4.i. Entry criteria include:

1. Age between 18 – 45 years
2. Currently on a stable two, three, four, or five times daily dose of sublingual BUP. Subjects participating in Part D during postpartum PRC visits must be taking Subutex or Suboxone.
3. Gestational age < 19 6/7 weeks *
4. Singleton gestation
5. Able to give informed consent and undergo study procedures
6. Willing to have urine samples screened for the presence of alcohol, barbiturates, opiates, cocaine (or metabolites), benzodiazepines, synthetic opioids and PCP *
7. Willing to participate in at least one PK study either during pregnancy or in postpartum *

*Requirement applies only to those subjects in the PK study

D.4.ii. Exclusion Criteria include:

1. Major fetal anomalies or malformations
2. HIV or AIDS

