Patients will be at steady state when the pharmacokinetic studies are performed. This will be documented by comparing the concentration at time 0 and at 12 hrs. (less than 20% variation). Plasma concentration-time profiles will be analyzed using both non-compartmental and population pharmacokinetic modeling and simulation approaches. Data will be analyzed using WINNONLIN and NONMEM software. We will compare various pharmacokinetic parameters between pregnant and non-pregnant (postpartum) subjects using a paired t-test as described previously. This will include all non-compartmental data (C_{max}, T_{max}, AUC(0-t), AUC(0-∞), k_e, λ_Z, CL/F, CLR, V_d/F, V_{ss}, AUMC, and MRT). Population pharmacokinetic model will be developed using nonlinear mixed effects modeling software (NONMEM version 7.1; ICON Development Solutions, [name]), GNU Fortran 95 compiler and PLT tools (version 5.1.0). The general linear model under steady state will be constructed using ADVAN5 SS5 subroutines. In order to identify the covariates that influence the pharmacokinetics of BUP, the following covariates will be evaluated: maternal age (years), body weight (kg), race, gestational age, serum albumin, serum creatinine (mg/dL), salivary PH, buprenorphine dose, tablet size and co-medications and SNPs of the various metabolizing enzymes. For covariate selection, univariate analysis with stepwise forward addition ($p < 0.01$) and backward elimination ($p < 0.001$) procedures will be followed. The covariates that significantly influence the pharmacokinetics of BUP and its metabolite will be incorporated in the final model. The predictive performance of the model will be internally evaluated using prediction corrected-visual predictive check, where 1500 data sets will be simulated using the parameter estimates in the final model. The 50th percentile concentration (median) and the 5th and 95th percentile concentrations (90% prediction interval) will be plotted and compared to the observed concentrations. The data obtained will be used to validate the predictions of SIMCYP-PBPK simulation from the basic/translation project.

D.6. Preliminary Data Relevant to the Primary Outcome

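### The primary AUC test is left open among three methods that, with only one PK study required per woman, would analyse different sets of women

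*Combined protocol and SAP*

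**What the plan says.** D.5.xiii, Data Analysis Plan, makes BUP AUC in early versus late pregnancy the primary outcome and adds comparisons with postpartum. On method: "Mixed-effect models, repeated measures ANOVA or paired t-testing, will be used to compare early to late-pregnancy and overall pregnancy values to the postpartum values". It gives no rule for choosing, no missing-visit rule and no analysis scale. It does not say how a pooled pregnancy value is formed for a woman with one pregnancy visit.

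The Secondary Hypotheses part of D.5.xiii names a method for a parameter list that includes AUC: "We will compare various pharmacokinetic parameters between pregnant and non-pregnant (postpartum) subjects using a paired t-test as described previously". It also plans a population model: "Population pharmacokinetic model will be developed using nonlinear mixed effects modeling software". That model is described for identifying covariates, not as the primary test.

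On attendance, D.1 plans three PK studies in each of 40 women but states that "subjects are only required to complete one PK study in order to participate in this portion of the study". D.4 (Part A) says "Subjects will participate in PK studies that will occur at 2-3 different times during the study", then also sets a minimum of one. Entry criterion 7 (D.4.i) reads "Willing to participate in at least one PK study either during pregnancy or in postpartum", so the single study may be postpartum. D.5.iii adds: "If non-prescribed opiates/opioids are detected during any PK screening visits, the subject will be ineligible to complete the pending PK visit". It softens this: "Subjects may be re-screened at a later date as long as they are within the gestational window for the PK visit".

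The Primary Hypothesis part gives a sample size of 37 plus 3 for dropout or noncompliance. For the physiologic outcomes it counts 2-3 PK studies per patient and concludes that there will be 120 studies.

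**The concern.** With complete data the three methods would largely agree. This protocol permits incomplete data and expects some. One PK study is enough, pregnancy visits must be 12 weeks apart, a positive screen blocks the pending visit, and D.7 warns that dropout may exceed that of most trials.

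The methods then use different women. A paired test describes only women who attended both compared visits, and it discards completed PK studies from the rest. Leaving the choice open means the primary analysis set, and possibly the primary result, could be settled after the data are known. For the pregnancy-versus-postpartum comparison the Secondary Hypotheses part already names the method that discards studies.

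**Working it through.** **1. The plan's 37.** Inputs from the Primary Hypothesis part: late-pregnancy mean 2.34, SD 1.82, alpha 0.05 (taken as two-sided), and the 0.80 read as power. A 50% difference is taken as 0.5 × 2.34 = 1.17. The unpaired formula gives n = 2 × [(1.960 + 0.842) × 1.82 / 1.17]² = 38.0, so 38 per time point. With the mean of 2.4 in D.6 (difference 1.20) it gives 36.1, so 37. A paired t-test also needs 37 pairs if both SDs are 1.82 and r = 0.1, or if the SDs are 1.82 and 2.8 and r = 0.5. The figure can be reached either way, and the plan does not say whether it counts women with both visits.

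**2. Reaching 37 pairs from 40 women.** The documents give no attendance rate; a is an assumed attendance per visit. If visits are missed independently, the number with both pregnancy visits is Binomial(40, a²). If a woman attends all or none, it is Binomial(40, a).

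| a | P(≥37), independent misses | P(≥37), all or none |
|---|---|---|
| 0.95 | 44% | 86% |
| 0.90 | 4% | 42% |

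These fix 40 women with no replacement.

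**3. Studies a paired test discards, a = 0.7.** Expected pregnancy studies: 80 × 0.7 = 56.
- Independent misses: 40 × 0.49 = 19.6 pairs, so 56 − 39.2 = 16.8 studies go unused. Only 40 × 0.343 = 13.7 women have all three visits for a classical ANOVA.
- All or none: 28 pairs, and nothing is discarded.

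**4. Power, early versus late.** Simulation of lognormal AUC with compound symmetry, 40 women, no replacement, ratio 1.5, 2,000 runs per scenario. The SDs in the Primary Hypothesis part imply a CV of 1.82/2.34 = 0.78 and 2.8/4.0 = 0.70; 0.74 is the midpoint. D.6 states 50%. The within-woman correlation r is assumed. Entries are raw paired t / log paired t / log mixed model, in percent. In the middle column a woman attends at all with probability √a, then each visit with probability √a.

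| Scenario | Independent misses | Half of each pattern | All or none |
|---|---|---|---|
| CV 0.74, r 0.3, a 0.7 | 47/56/72 | 55/66/74 | 63/74/75 |
| CV 0.74, r 0.5, a 0.7 | 58/71/84 | 69/81/88 | 78/89/90 |
| CV 0.74, r 0.3, a 0.9 | 70/81/86 | 74/83/87 | 76/85/86 |
| CV 0.50, r 0.3, a 0.7 | 80/85/95 | 87/91/96 | 93/95/96 |

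In the first cell the mixed-model gain over the log paired test is 72 − 56 = 16 points. A 6,000-run repeat puts that log paired test at 58.7%, which makes the gain about 13. At 90% attendance the gains are 5, 4 and 1 points. In the all-or-none column they are about 1 throughout.

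**5. How much lost pairs matter.** With constant SD 1.82 and difference 1.17, the SD of the paired difference is 1.82 × √(2(1 − r)). Twenty pairs give 64% power at r = 0.3 and 78% at r = 0.5; 28 pairs give 79% and 91%. At r = 0.5, 21 pairs reach 80%.

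**6. Study count for the physiologic outcomes.** 40 × 3 = 120; 40 × 2 = 80; 40 × 1 = 40. The plan's 2-3 per woman gives 80 to 120, and its required minimum gives 40.

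**The case against.** The strongest reply is that attendance may be good and power adequate whichever method is used. D.1 says women will be encouraged to complete as many studies as possible. D.5.iii replaces women dismissed from their treatment clinic for non-compliance or after two positive opioid screens. D.7 offers incentives and lets mothers bring their babies. PK women must enter before 19 6/7 weeks, so a postpartum-only participant is permitted but is not the planned path. All of this stands. Replacement in particular makes the figures above pessimistic to an unknown degree. At CV 0.50, every paired power shown is at least 80% even at 70% attendance. If the 50% difference means a ratio of 2, every paired power is at least 90% at CV 0.74 and 70% attendance. None of it selects the primary test.

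It is also fair that the log-scale advantage follows partly from simulating lognormal data, and that the mixed model was tried only under the covariance it assumes.

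A reader might infer that 120 is an arithmetic error that undermines the sample size. The documents do not support that. It equals the three-visit plan of D.1 carried out in full, and it supports only the secondary physiologic outcomes. D.3 already warns that the sample may be inadequate for some secondary questions. What remains is that a firm 120 does not follow from 2-3 studies per woman.

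**Conclusion.** The point holds as a gap in prespecification and should be fixed. The method for the primary comparison is not chosen, and two of the three options discard completed PK studies that the protocol's own attendance rules make likely to be unpaired. That conclusion needs no assumption about attendance.

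The size does. At CV 0.74, ratio 1.5 and r 0.3, with 40 women and no replacement, the mixed model gains about 13 to 16 points over a log paired t-test at 70% attendance with independent misses, about 1 to 5 at 90%, and about 1 if women miss all visits or none. Attendance, missed-visit pattern and r are all absent from the documents.

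A reader might go further and infer that the trial is underpowered. The documents do not establish this: they project no attendance, they provide for replacement, and at r of about 0.5 some 21 pairs would suffice under a constant SD. Nor should the mixed model be read as a cure for missing visits. It assumes they are missing at random, which may fail when a positive opioid screen blocks a visit and is also related to exposure. Paired tests do not escape that problem.

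**What to change.** - Prespecify one primary analysis: a linear mixed model on log dose-adjusted AUC, with visit (early, late, postpartum) as fixed effect and woman as random effect, using every completed PK study. Mixed models are already among the plan's options; the log scale and visit coding would be new.
- Define the pooled pregnancy value as a stated contrast, such as the average of the early and late model means.
- Use the same model for the AUC comparison under Secondary Hypotheses, and keep paired tests as sensitivity analyses.
- State whether 37 means women with both visits.
- List missed visits by reason.
- In the Primary Hypothesis part, give the physiologic study count as up to 120 (80 to 120 at 2-3 studies per woman, 40 at the required minimum).

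The cost is protocol wording and slightly more analysis, with no extra patients or procedures. The log scale moves the target to geometric mean ratios, whereas the sample size was built on arithmetic means; the plan should say so. The missing-at-random assumption should be stated with the model.
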